The purpose of this study is to compare SARS-CoV-2 results from clinical specimens on the ID NOW and the Accula systems. If the Accula system is comparable or demonstrates superior test parameters including sensitivity, then this assay may potentially be used throughout Ascension, especially in markets which have limited access to testing. This in turn will assist in improving turnaround times for COVID-19 results and facilitate reinstating elective surgeries.

Methods:

All testing will be conducted in a College of American Pathologists (CAP)- accredited biosafety level-2 laboratory with restricted access. All patient specimens will be manipulated under a certified biosafety level-2 cabinet.

The testing personnel for the ID NOW will be medical laboratory technologists and technicians in the clinical microbiology laboratory who have previously been trained and are competent under Clinical Laboratory Improvement Amendments (CLIA) guidelines at performing the ID NOW COVID-19 assay. Testing personnel for the Accula assay will consist of a lead medical laboratory scientist and the technical director of the microbiology laboratory, a Ph.D. level scientist.

The ASJ microbiology laboratory validated the ID NOW COVID-19 assay in April 2020. The protocol for testing is located on PolicyStat and can be accessed using the link below. https://ascension-lab.policystat.com/policy/7897941/latest/. Currently when rapid COVID-19 tests are ordered on ASJ ED patients or inpatients one nasal swab is collected by the clinical staff. The swab is then placed in a sterile conical tube and delivered to the microbiology laboratory where the COVID-19 test is run STAT on the ID NOW. Specimens used for ID NOW testing cannot be re-used for repeat ID NOW testing or any other laboratory testing due to the initial genomic extraction step which requires use of the entire swab.

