Patients with orders for rapid COVID-19 testing who have consented to participate will be included in the study. We will also include patients who have been confirmed positive for COVID-19 by PCR, swabs will be collected from these patients after obtaining consent. For patients with orders for rapid COVID-19 testing, one additional clinical specimen, anasal specimen will be collected from the patient at the same time as the initial specimen for the ID NOW. For patients who were confirmed positive by PCR, two additional swabs will be collected: one for the ID NOW and one for the Accula test. Swabs for both ID NOW and Accula testing will be provided to the clinical teams in pre-packaged kits with directions on specimen collection and transport. After collection, all swabs must be labeled with a specimen label (per current protocol). Following consent and collection of specimens, specimens will be sent to the microbiology laboratory. The ID NOW COVID-19 assay will continue to be performed STAT.

If laboratory testing personnel are available, the additional swab will be eluted in a buffer tube as recommended by the manufacturer and then utilized for the Accula SARS-CoV-2 assay. In the event that immediate testing cannot be performed, however, swabs will be stored at room

temperature for two hours or 2-8°C for up to 24 hours prior to testing on the Accula (per manufacturer's guidelines). The Accula system is a new platform for the microbiology laboratory. The manufacturer of the Accula Test, Mesa Biotech, has been working in conjunction with the National Ascension Laboratory team to pilot this study in two Ascension Markets (Michigan and Florida). Five Accula analyzers will be sent to the Ascension Michigan Clinical Microbiology Laboratory along with SARS-CoV-2 test kits. The protocol for testing will strictly follow the manufacturer's instructions (https://www.fda.gov/media/136355/download).

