If there is a discrepancy between the ID NOW and Accula test results, an additional specimen (nasal) will be collected from the patient, if possible (i.e. if the patient remains in-house) to confirm the COVID-19 results (unless the PCR results are already available). This additional test must be more sensitive than POCs. If the ASJ molecular laboratory is able to complete validation on the Roche 8800 which will be arriving on April 24, 2020, the additional specimen will be run with the Roche COVID-19 assay. If not, specimens will be sent out to a reference laboratory for confirmation COVID-19 testing.

This study will evaluate accuracy (correlation) by comparing Accula results to the ID NOW, precision (reproducibility) by repeating select specimens with different users and on different analyzers, limit of detection by diluting commercial SARS-CoV-2 controls with a known concentration and cross-reactivity by testing known respiratory viruses (including influenza A, B and RSV) on the Accula.

Data Management and Analysis:

The electronic data from this study will be stored on the Ascension network which is a password-protected encrypted computer drive. All HIPAA guidelines will be followed to protect patient information. Only the lead technologist and technical director will have access to this file.

Currently, patient results from the ID NOW test are entered in the laboratory information system (LIS) by microbiology staff. Since the ID NOW is not interfaced with the LIS, patient reports are printed prior to verification and the hardcopies are stored in a binder in the laboratory. As required by CAP, these documents are stored securely in the laboratory for two years.

The lead technologist or technical director will enter the ID NOW results into the secure data file using the ID NOW hardcopy reports. The results from the Accula test and the Roche or send-out test, if performed, will be entered into the same spreadsheet using the same barcode number as the ID NOW. The only patient demographic information that will be recorded in the spreadsheet is the specimen barcode number for the ID NOW.

Any subsequent data shared with individuals other than the study testing personnel will not contain any patient identifiers, including the specimen barcode used as the identifier in the data collection file.

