The following test parameters for the Accula will be calculated using the ID NOW as a comparator: sensitivity, specificity, positive-predictive value, negative predictive value.

Sample Size and Duration of Study:

The aim is to test 100 unique patients. The duration of this study will be determined based upon the number of specimens collected daily. We anticipate that sufficient specimens will be collected within a one-week time period.

Predicted Results:

The Accula SARS-CoV-2 test parameters including sensitivity, specificity, positive-predictive value, and negative predictive value will be similar or superior to the ID NOW COVID-19 assay.

References:

- 1. Accula SARS-CoV-2 Test IFU (EUA). Mesa Biotech, 2020.
- 2. ID NOW COVID-19 Assay IFU (EUA). Abbott, 2020.
- 3. Interim Guidelines for Collecting, Handling, and Testing Clinical Specimens from Persons for Coronavirus Disease 2019 (COVID-19). CDC. Last accessed 20 April 2020.
 - https://www.cdc.gov/coronavirus/2019-ncov/lab/guidelines-clinical-specimens.html
- 4. Laboratory testing for 2019 novel coronavirus (2019-nCoV) in suspected human cases: Interim guidance. World Health Organization. 19 March 2020.

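### The question is head-to-head, but the planned calculation yields no Accula-minus-ID NOW difference or interval, and no limit governs when 'similar' may be claimed

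*Combined protocol and SAP*

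**What the plan says.** The aim is comparative and tied to a decision. Purpose states: "If the Accula system is comparable or demonstrates superior test parameters including sensitivity, then this assay may potentially be used throughout Ascension". Predicted Results expects that the four Accula parameters "will be similar or superior to the ID NOW COVID-19 assay". Neither 'comparable' nor 'similar' is given a number.

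The design is paired. For patients with a rapid-test order, Methods says the extra nasal swab "will be collected from the patient at the same time as the initial specimen for the ID NOW". For patients already confirmed positive by PCR, "two additional swabs will be collected: one for the ID NOW and one for the Accula test".

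On analysis, Methods says: "This study will evaluate accuracy (correlation) by comparing Accula results to the ID NOW", without naming a statistic. Data Management and Analysis says: "The following test parameters for the Accula will be calculated using the ID NOW as a comparator", and lists sensitivity, specificity and the two predictive values. Methods also plans precision, limit of detection and cross-reactivity work, and a more sensitive test on discrepant pairs where a further specimen can be obtained. On size: "The aim is to test 100 unique patients". No between-assay difference, interval, test, margin or acceptance limit is stated.

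**The concern.** A claim that one assay is similar or superior to another needs three things: an estimate of the difference, a measure of its uncertainty, and a limit on the deficit that can still be called similar. The plan collects the data for the first two but computes neither, and it does not set the third.

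At stake is an ungoverned conclusion. After the data are in, any Accula figure could be called comparable or not comparable, and the word 'superior' has no calculation behind it. Background describes ID NOW's own sensitivity as low, so a further undetected loss would matter, and so would a real gain that the calculation cannot show.

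**Working it through.** **1. What the planned calculation can show.** Cross-classify the patients: *a* positive on both assays, *b* positive on ID NOW only, *c* positive on Accula only, *d* negative on both. With ID NOW as reference, for the Accula:

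- sensitivity = a/(a+b)
- specificity = d/(c+d)
- PPV = a/(a+c)
- NPV = d/(b+d)

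ID NOW scored against itself is 100% on all four, so the Accula can at best tie. An infected patient found only by the Accula falls in *c*, counts as a false positive, and lowers specificity and PPV. The head-to-head contrast in infected patients, (c − b)/n, appears nowhere, although both discordant counts will be in the table.

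**2. The stated size.** The figure of 100 cannot be reproduced or called wrong: no alpha, power, expected sensitivity, number of positives, discordance rate or margin is given.

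**3. Illustration (all inputs assumed).** Take n = 30 PCR-positives, ID NOW sensitivity 80%, Accula 70%.

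- Independent misses: b-probability 0.80 × 0.30 = 0.24; c-probability 0.20 × 0.70 = 0.14; discordance 0.38.
- Halfway to fully nested misses (full nesting is 0.10 and 0): 0.17 and 0.07; discordance 0.24.

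Probability that a two-sided exact McNemar test at 0.05 is non-significant despite the true 10-point deficit:

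| PCR-positives | Independent | Half-nested |
|---|---|---|
| 20 | 95% | 96% |
| 30 | 92% | 90% |
| 40 | 88% | 85% |
| 50 | 85% | 79% |

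**4. Precision when the assays are equal.** At 80% each, total discordance ψ is 0.32 (independent) or 0.16 (half-nested). The approximate half-width is 1.96 × √(ψ/n). At n = 30 this gives 0.202 and 0.143. The simulated mean Wald half-widths are 0.197 and 0.137, that is, about 14 to 20 points.

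**5. Positives needed for a given limit.** With true difference 0, one-sided 0.025 and 80% power, n = (1.96 + 0.84)² × ψ / limit². The limits below are illustrations, not proposals.

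| Limit | ψ = 5% | ψ = 10% | ψ = 20% |
|---|---|---|---|
| 15 points | 18 | 35 | 70 |
| 10 points | 40 | 79 | 157 |
| 5 points | 157 | 314 | 628 |

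With 100 patients in all, a 5-point limit is out of reach across this range. A 10-point limit needs low discordance and many positives.

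**6. Which patients can supply the difference.** Rapid-order patients have PCR sought only when the assays disagree, so their concordant positives have no planned PCR. Suppose 30 PCR-confirmed patients are pooled with 20 infected rapid-order patients, under the assumptions of step 3. The expected net deficit is 0.10 × 50 = 5 patients. The denominator is 30 plus only the discordant rapid-order patients:

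- independent: 5 / (30 + 20 × 0.38) = 5 / 37.6 = 13.3 points
- half-nested: 5 / (30 + 20 × 0.24) = 5 / 34.8 = 14.4 points

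A true 10-point deficit is inflated to about 13 to 14 points. The groups should not be pooled.

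**The case against.** The strongest reply is that the plan names no significance test and no side-by-side comparison of two PCR-based sensitivities, so the McNemar probabilities describe an analysis it does not contain. That stands. They show why non-significance should be ruled out as a route to 'similar', not what the plan will do.

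A reader might go further and infer that 'comparable' is the default finding whatever the truth. The documents do not support this. In the scenario of 30 positives at 80% and 70%, the planned figure a/(a+b), taken over those positives, averages 70% (0.56/0.80) to 79% (0.63/0.80) and reaches 90% in only about 1% to 9% of studies. Even a truly equal Accula would average 80% to 90%. The planned number tends to make the Accula look worse, not falsely similar.

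Nor is it right to infer that the pairing is ignored or that four parameters are the whole output. The planned rates come from the paired table, and Methods lists further evaluations. What is absent is the paired difference, its interval and a limit.

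Finally, this is a pilot, and Purpose speaks only of potential use. That lowers the stakes, but the remedy needs no extra patients.

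**Conclusion.** The point holds in a limited form. The plan asks a comparative question; its accuracy calculation cannot show superiority, yields no between-assay difference or interval, and leaves 'similar' and 'comparable' without a limit. This follows from the text alone.

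The size is illustrative, because the number of positives, the two sensitivities and the dependence between misses are all assumed. At 30 PCR-positives, a 10-point deficit would be non-significant in about 90% to 92% of studies, and equal assays would give an interval of about plus or minus 14 to 20 points. The risk shrinks as positives increase. The documents do not show that a false claim of comparability is likely, only that nothing governs the claim. The change is worth making before the first specimen but does not threaten the data.

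**What to change.** In Data Management and Analysis:

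1. In patients enrolled as PCR-confirmed positive, report the paired difference in detection rate, Accula minus ID NOW = (c − b)/n, with both discordant counts and a paired 95% interval (Tango or Newcombe).
2. Add enrolment group (PCR-confirmed or rapid-order) to the data file. The listed contents do not include it.
3. Do not pool rapid-order patients into this difference. Report them separately as positive and negative agreement with ID NOW.
4. State that comparability will not be inferred from close point estimates or a non-significant test. Before the first specimen, the laboratory writes down the largest deficit it would accept. If the lower limit of the interval allows a larger deficit, the result is reported as 'comparability not shown'.

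The cost is a few lines, one data column and a short calculation, with no added patients or swabs. There are two limits. At this size the conclusion may well be 'not shown'. And the change addresses detection in known positives only: a matching comparison of specificity, or of sensitivity in rapid-order patients, would need PCR on concordant pairs as well, which is a larger change.
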